2.0 Statement of the Problem

Approximately 830 women die each day worldwide from preventable causes related to pregnancy and childbirth, and almost all of these deaths occur in low-resource settings.^{5,6} Approximately 2.7 million neonates die per year,⁷ and an additional 2.6 million are stillborn.⁸ Early ascertainment of fetal gestational age is critical to good clinical management, as is detection of clinical obstetric conditions that put both mothers and fetuses at increased risk of morbidity and mortality. Ultrasound improves GA estimation and can provide detailed

information on fetal wellbeing and maternal conditions, thus identifying high-risk pregnancies and enabling informed decisions around patient management (Table 1). Despite these well-described benefits, obstetric sonography is not available to the majority of the world's pregnant women.⁹

Table 1: Obstetrical diagnoses facilitated by sonography

Diagnosis	Proportion of pregnancies affected	Adverse maternal outcomes	Adverse fetal or neonatal outcomes
Ectopic pregnancy	0.015 ¹⁰	Hemorrhage, death	-
Twin or triplet gestation	0.013 ¹¹	Preeclampsia, hemorrhage, death	Prematurity, perinatal death
Placenta previa, accreta, vasa previa	0.005 ¹²	Hemorrhage, death	Anoxic brain injury, perinatal death
Fetal malpresentation	0.038 ¹³	Obstructed labor, fistula, pelvic trauma, sepsis, hemorrhage, death	Anoxic brain injury, perinatal death
Fetal growth restriction	0.10 ¹⁴	-	Anoxic brain injury, perinatal death
Macrosomia ($\geq 4,000\text{g}$)	0.08 ¹⁵	Obstructed labor, fistula, pelvic trauma, sepsis, hemorrhage, death	Birth trauma, peripheral nerve injury, anoxic brain injury, perinatal death
Oligohydramnios	0.11 ¹⁶	-	Perinatal death
Polyhydramnios	0.01 ¹⁷	Respiratory compromise, hemorrhage, death	Prematurity, perinatal death
Pre-term birth	0.11 ¹⁸	-	Prematurity, neonatal death
Post-term pregnancy	0.004-0.07 ¹⁹	Obstructed labor, fistula, pelvic trauma, sepsis	Anoxic brain injury, meconium aspiration syndrome, perinatal death
Intrauterine fetal death	0.0184 ²⁰	Coagulopathy, sepsis, hemorrhage, death	-
Retained placenta	0.02 ²¹	Sepsis, hemorrhage, death	-

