6.3 Study visit procedures

6.3.1 Screening and Randomization

In Zambia, our recruitment activities will begin with community sensitization in the catchment area of the recruitment clinics to educate community members about the study and encourage early presentation for ultrasound. This community and clinic sensitization will be underway prior to initiation of this protocol as a result of other programs ongoing in the catchment areas. In North Carolina, we will advertise the study through flyers, posters, and other electronic or written materials.

Study staff will approach potentially eligible women – either in groups or individually – to inform them about the study (including eligibility criteria). Staff will provide interested women with additional information and referrals to the study clinic for eligibility assessment.

All protocol-specified ultrasound procedures will occur after 13 completed gestational weeks (i.e., 14 0/7 weeks or greater). To be eligible for study participation, women must have documentation of a baseline scan conducted by a trained sonographer prior to 14 weeks gestation to confirm pregnancy location, viability, and gestational age by crown-rump length.

After completing the study informed consent process, study staff will gather targeted information on demographics, health and risk behaviors, medical and obstetrical history, medication use, stress, and nutrition. Participants will undergo blood pressure assessment and anthropometry, including height, weight, mid-upper arm circumference (MUAC), and fundal height (FH). Blood and urine will be collected as detailed in Table 3.

Following final confirmation of eligibility, participant will be assigned a date for each of their follow-up visits in a fashion that ensures approximately equal distribution of study visits across the GA range within each designated visit window. For instance, the primary evaluation window comprises the 14-week period between 14⁰/₇ and 27⁶/₇ gestational weeks, inclusive. Thus, through the randomization procedure, a participant will have a 1 in 14 chance of being allocated to a given gestational week within the primary evaluation window (Table 2). A statistician not otherwise associated with the study will design the scheme and pre-generate the visit schedules for each participant prior to study commencement. Women will be allowed to choose their preferred day of participation within the randomized week.

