Participants who are randomly allocated to a follow-up visit schedule who do not complete visit 1.0 for any reason (e.g., because they deliver prior to the target window or do not return for the visit) will count as screened but will not count toward the overall enrollment target of 400 participants.

Table 2: Random visit allocation

Primary Evaluation Window	Gestational Week	GA Range (days)	Number allocated	Secondary Evaluation Windows	Gestational Week	GA Range (days)	Number allocated
	14 ⁰ - 14 ⁶	98 - 104	28		28 ⁰ - 28 ⁶	196 - 202	44
	15 ⁰ - 15 ⁶	105 - 111	28		29 ⁰ - 29 ⁶	203 - 209	44
	16 ⁰ - 16 ⁶	112 - 118	28		30 ⁰ - 30 ⁶	210 - 216	44
	17 ⁰ - 17 ⁶	119 - 125	28		31 ⁰ - 31 ⁶	217 - 223	44
	18 ⁰ - 18 ⁶	126 - 132	28		32 ⁰ - 32 ⁶	224 - 230	44
	19 ⁰ - 19 ⁶	133 - 139	28		33 ⁰ - 33 ⁶	231 - 237	45
	20 ⁰ - 20 ⁶	140 - 146	29		34 ⁰ - 34 ⁶	238 - 244	45
	21 ⁰ - 21 ⁶	147 - 153	29		35 ⁰ - 35 ⁶	245 - 251	45
	22 ⁰ - 22 ⁶	154 - 160	29		36 ⁰ - 36 ⁶	252 - 258	45
	23 ⁰ - 23 ⁶	161 - 167	29				
	24 ⁰ - 24 ⁶	168 - 174	29		37 ⁰ - 37 ⁶	259 - 265	100
	25 ⁰ - 25 ⁶	175 - 181	29		38 ⁰ - 38 ⁶	266 - 272	100
	26 ⁰ - 26 ⁶	182 - 188	29		39 ⁰ - 39 ⁶	273 - 279	100
	27 ⁰ - 27 ⁶	189 - 195	29		40 ⁰ - 40 ⁶	280 - 286	100

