6.3.2 Study follow-up

At each study follow-up visit, research staff will collect interval medical and obstetric history, perform anthropometry, measure blood pressure and fundal height, and collect blood and urine specimens for storage and future approved testing (Table 3). An untrained operator will conduct blind sweep procedures using both a commercial ultrasound machine and an approved portable low-cost device. More than one low-cost device may be used for data collection. Next, the sonographer will perform full standard biometry procedures and additional protocol-related ultrasound sweeps using a commercial ultrasound machine. Finally, the trained sonographer will perform biometry and blind sweeps with the low-cost device.

NB: The FAMLI Technology software will not be used to assess gestational age at the time of novice or trained sonographer assessment in an effort to avoid biasing sonographer data collection during biometry. We will also train sonographers not to ask participants their due date or last menstrual period prior to commencing the study scan.

All participants will be followed through delivery. Study staff will document gestational age, vital status, birthweight, and sex at delivery through a combination of medical record review

and participant interview as needed. This visit may occur over the phone or in person. Based on the timing of delivery, not all participants may complete all three planned study follow-up visits.

TABLE 3: Schedule of Evaluations

Visit Number	0.0	1.0	2.0	3.0	4.0
Gestational Age (weeks)	<14	14-27 ⁶	28-36 ⁶	37-40 ⁶	Delivery
ADMINISTRATIVE / REGULATORY PROCEDURES					
Informed consent	•				
Confirmation of eligibility	•				
Collection / review of locator info	•	•	•	•	•
Randomization of visit timing	•				
CLINICAL / BEHAVIORAL PROCEDURES					
Obstetrical and medical history	•	•	•	•	•
Anthropometry	•	•	•	•	
Blood pressure measurement	•	•	•	•	
Fundal height measurement	•	•	•	•	
Physical exam	•				
Untrained operator scan		•	•	•	
Trained sonographer scan		•	•	•	
LABORATORY PROCEDURES					
Urine storage	•	•	•	•	
Blood storage	•	•	•	•	

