6.6 Biological specimen collection

All samples will be obtained from study participants by trained clinical staff according to approved standard operating procedures. Biological samples (i.e., blood and urine) will be used for untargeted metabolomics and other multi-omic analyses to identify metabolites, proteins, transcripts, and host genetic factors associated with fetal maturation, gestational age, parturition timing, and adverse outcomes. Each study site will house its own biological samples and make plans for off-site redundancy in case of power failures or freezer malfunction. Lab testing will be conducted in parallel with the primary analysis and will take advantage of the excellent gestational age dating available for all participants and the even distribution of sample collection across the gestational age spectrum.

Use of stored specimens for testing that is not specifically designated in this protocol as described above will require additional regulatory approval. Separate written informed consent for specimen storage and future use will be specifically obtained during the informed consent process.

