To ensure fair comparison, the analysis will be restricted to only those cases where both the index test and clinical reference standard (expert biometry) are available; hence, we have paired estimates of the two methods. This means that for the primary study outcome, the difference in the MAEs of the two approaches corresponds to the mean of the pairwise difference in absolute errors, m . Study visits that are missing a gestational age estimate from either the index test or the clinical reference standard will be excluded. Potential reasons for missingness include when the index test model indicates a failure to calculate GA based on the blind sweeps of that study, patient non-attendance of a scheduled study visit, and data loss. By design, participants who experience a pregnancy loss after screening but before visit 1 will be excluded from the DXA Study (and therefore from analysis) and replaced with other participants to be enrolled.

As secondary analysis, we will present the difference in root mean squared error and Wald-type 95% confidence interval. Also, as secondary analysis, we will plot the empirical cumulative distribution function for the absolute error produced by the index test and expert biometry. We will present the difference in proportions with absolute error below 7 and 14 days between the index test and expert biometry, along with Wald-type 95% confidence intervals. The primary analysis compares the index test to the clinical reference standard in the pre-defined primary evaluation window (Figure 1). In secondary analyses we will make the same comparison in two

secondary windows, defined (a) between 28⁰/₇ and 36⁶/₇ weeks of gestation, inclusive (visit 2) and (b) between 37⁰/₇ weeks and 40⁶/₇ weeks, inclusive (visit 3).

Figure 1: Gestational age definitions of the primary and secondary evaluation windows

GA	Enroll													Primary Evaluation Window										Secondary Evaluation Windows																														
	1	2	3	4	5	6	7	8	9	10	11	12	13	14	15	16	17	18	19	20	21	22	23	24	25	26	27	28	29	30	31	32	33	34	35	36	37	38	39	40														
<12 ⁰													14 ⁰ to 27 ⁶														28 ⁰ to 36 ⁶														37 ⁰ to 40 ⁶													

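### Equal spread holds for allocated term dates, not completed visits: delivery thins the later weeks, so the pooled visit-3 result mainly describes weeks 37-38

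*Protocol*

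**What the plan says.** Protocol section 6.3.1 states that dates are assigned "in a fashion that ensures approximately equal distribution of study visits across the GA range within each designated visit window". Table 2 carries this out with equal numbers per week inside each window. The last term row reads "40 ⁰ - 40 ⁶ 280 - 286 100", and weeks 37, 38 and 39 also have 100 each. Schedules are generated before the study starts and given out at visit 0.0, before 14 weeks (Table 3). The day is left open: "Women will be allowed to choose their preferred day of participation within the randomized week". Only women who miss visit 1.0 fall outside the target of 400; there is no such rule for visits 2 and 3.

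Section 6.3.2 does recognise the effect of delivery: "Based on the timing of delivery, not all participants may complete all three planned study follow-up visits". Section 6.9 gives 1,200 scans as an upper limit. Section 6.6 nevertheless has the laboratory work draw on "the even distribution of sample collection across the gestational age spectrum".

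The SAP says "In secondary analyses we will make the same comparison in two" secondary windows, the second being the whole of 37 0/7 to 40 6/7 weeks at visit 3. It analyses visits that have both estimates, and its examples of why one might be missing do not name delivery before visit 2 or 3. Both documents provide for censoring weights if loss to follow-up exceeds 9%; the SAP adds that selection bias must be suspected.

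**The concern.** A woman can be scanned at visit 3 only if she is still pregnant on a date fixed months earlier. The chance of that can only fall from week 37 to week 40. The week-40 slot opens on day 280, which section 4.0 gives as the conventional due date. Equal allocation therefore cannot produce equal numbers of completed visits in this window.

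What is at stake is the meaning of the visit-3 result. Section 4.0 says biometry error grows with gestational age, and section 6.8.1 reports MAE, RMSE and the within-7-day proportion for each test separately. If the completed scans cluster at 37-38 weeks, biometry's pooled term figures will tend to look better than they would over an even 37 0/7 to 40 6/7 spread, and the pooled number will say little about week 40. A reader given only that number and Table 2 would not see this.

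**Working it through.** **Step 1: the plan's own figures.** Table 2 adds up as intended: primary window 6×28 + 8×29 = 400; second window 5×44 + 4×45 = 400; term window 4×100 = 400; total 1,200.

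**Step 2: inputs for completed visits.**
- Delivered before 37 weeks (day 259): 0.11 ("Pre-term birth 0.11 ¹⁸", protocol Table 1).
- Post-term: 0.004 to 0.07 (same table). I take post-term as undelivered at 42 weeks (day 294), and add 0.02 as an assumed middle value.
- Both are background rates, not trial assumptions. The distribution by week within term is not given, so several shapes are used.
- No loss other than delivery.

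**Step 3: formula.** Expected completed visits in a week = 100 × the mean, over its seven days, of P(still pregnant on that day).

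**Step 4: delivery curves.**
- (a) Normal, fitted to the two background rates: SD = 35 / (z_post + 1.2265); mean = 259 + 1.2265 × SD. For 0.4% post-term, SD = 35 / (2.652 + 1.2265) = 9.0 and mean = 270.1 days. For 2%, 10.7 and 272.1. For 7%, 35 / (1.476 + 1.2265) = 13.0 and 274.9.
- (b) 11% preterm, the rest uniform from day 259 to day 294, with 0% or 7% left at day 294.
- (c) 11% preterm, the rest a normal truncated at day 259 with assumed mean 274, 277 or 280 days and SD 8, 9 or 10 days.

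**Step 5: results** (entries rounded separately; rows for (c) are a selection that includes the extremes).

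| Curve | Wk 37 | Wk 38 | Wk 39 | Wk 40 | Total of 400 | Wks 37-38 | Wk 40 share |
|---|---|---|---|---|---|---|---|
| Allocated | 100 | 100 | 100 | 100 | 400 | 50% | 25% |
| (a) post-term 0.4% | 81 | 55 | 26 | 8 | 170 | 80% | 5% |
| (a) post-term 2% | 82 | 61 | 36 | 16 | 195 | 74% | 8% |
| (a) post-term 7% | 84 | 67 | 47 | 27 | 224 | 67% | 12% |
| (b) 0% left | 81 | 64 | 46 | 28 | 219 | 66% | 13% |
| (b) 7% left | 82 | 66 | 49 | 33 | 229 | 64% | 14% |
| (c) mean 274, SD 9 | 84 | 66 | 39 | 15 | 205 | 74% | 8% |
| (c) mean 277, SD 9 | 86 | 74 | 49 | 23 | 233 | 69% | 10% |
| (c) mean 280, SD 8 | 88 | 81 | 61 | 32 | 263 | 64% | 12% |
| (c) mean 280, SD 10 | 87 | 78 | 59 | 35 | 259 | 64% | 13% |

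Overall loss runs from 1 − 263/400 = 34% to 1 − 170/400 = 58%; with fit (a) alone it is 44% to 58%. Week-40 loss runs from 65% to 92%. Day choice matters: if every woman came on the first day of her week, week-40 loss would be 55-86%; on the last day, 74-96%.

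**Step 6: the second window.** Visit 2 is little affected. Even if all 11% of preterm births were spread evenly from 28 to 37 weeks, about 400 × (1 − 0.11/2) = 378 visits would remain.

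**Step 7: would the censoring weights restore the spread?** If delivery counts as loss, 0.11 already exceeds the 9% trigger before the term window opens. But neither document says that it counts, and SAP Table 1 does not list assigned week among the possible covariates. Weights built on those covariates alone would not bring the weeks back to equal shares.

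**The case against.** The fair reply has several parts.

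- The sentence in section 6.3.1 governs assignment, and Table 2 is labelled as allocation. Together with the warning in section 6.3.2 and the upper limit in section 6.9, this shows that the authors knew visits would be lost. That stands: a reader might infer that the protocol overlooks delivery, and it does not. What it lacks is any expected yield, or a statement that the loss falls on the later term weeks.
- A reader might say flatly that half of the term visits and nearly all of the week-40 visits disappear. The documents do not support point claims. Half lies inside the range, but nearly all of week 40 is reached only at the lowest post-term rate.
- A reader might infer that the visit-3 comparison is biased. The comparison is a paired difference, and only a trend that differs between the methods would move it. The documents give no such trend. The effect on each method's own MAE may also be modest. Under fit (a) the mean assigned week of completed visits falls 0.43 to 0.73 below the balanced 38.5. If MAE rose by 0.5 day per week (an assumption), that is 0.2 to 0.4 day.
- Averaging over women still pregnant is a legitimate target, since delivered women cannot be scanned. Equal-week weighting is therefore not required, and it costs precision. Effective n = 1 / Σ(0.25²/n_w) is 83 to 187 under fit (a), against 170 to 224 unweighted.
- Harm to the biomarker objective is not shown. Section 6.6 speaks of the whole gestational range, and Table 2 is already uneven across windows (28-29, then 44-45, then 100 per week).
- Equivalence power is not the main issue. Protocol Table 4 gives 100% at N=200 and zero difference, although from second-trimester inputs.

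**Conclusion.** The point holds as one about the stated property of the design and the reach of a secondary result. Equal spread is a feature of the allocation and will not carry through to completed term visits. The direction needs only that dates are fixed early, that delivered women cannot be scanned, and that there is no replacement after visit 1.0. The size rests on assumed delivery curves and no other drop-out: about one third to three fifths of term visits lost. That the pooled visit-3 result is mainly a 37-38 week result survives every curve tried.

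The expected consequence is that biometry's own pooled term MAE, RMSE and within-7-day figures look somewhat better than over an even spread. Nothing in the documents shows which way, if at all, the paired difference would move. The primary outcome and the sample size rest on 14 0/7 to 27 6/7 weeks and are unaffected. This is a minor-to-moderate point.

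**What to change.** 1. In protocol section 6.3.1 (text and Table 2) and section 6.6, say that equal spread applies to allocation and is not expected of completed term visits. Give the expected term yield as a range with its assumptions; on the curves above, about 170 to 263 of 400, with about 8 to 35 in week 40.
2. In the SAP, report visit-3 results by gestational week with the number of completed paired scans, beside the pooled estimate, merging weeks 39 and 40 if sparse. A week-standardised estimate may be added as a sensitivity analysis, with its wider interval stated.
3. State whether delivery before a scheduled visit counts towards the 9% trigger. If it does, include assigned week in the weight model.
4. Word the visit-3 conclusion as applying to undelivered pregnancies, mostly at 37-38 weeks.

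The cost is some wording, one extra table and a less favourable statement of term coverage. No visit or procedure changes.

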6.3.2 Study follow-up

At each study follow-up visit, research staff will collect interval medical and obstetric history, perform anthropometry, measure blood pressure and fundal height, and collect blood and urine specimens for storage and future approved testing (Table 3). An untrained operator will conduct blind sweep procedures using both a commercial ultrasound machine and an approved portable low-cost device. More than one low-cost device may be used for data collection. Next, the sonographer will perform full standard biometry procedures and additional protocol-related ultrasound sweeps using a commercial ultrasound machine. Finally, the trained sonographer will perform biometry and blind sweeps with the low-cost device.

NB: The FAMLI Technology software will not be used to assess gestational age at the time of novice or trained sonographer assessment in an effort to avoid biasing sonographer data collection during biometry. We will also train sonographers not to ask participants their due date or last menstrual period prior to commencing the study scan.

All participants will be followed through delivery. Study staff will document gestational age, vital status, birthweight, and sex at delivery through a combination of medical record review

and participant interview as needed. This visit may occur over the phone or in person. Based on the timing of delivery, not all participants may complete all three planned study follow-up visits.

TABLE 3: Schedule of Evaluations

Visit Number	0.0	1.0	2.0	3.0	4.0
Gestational Age (weeks)	<14	14-27 ⁶	28-36 ⁶	37-40 ⁶	Delivery
ADMINISTRATIVE / REGULATORY PROCEDURES					
Informed consent	•				
Confirmation of eligibility	•				
Collection / review of locator info	•	•	•	•	•
Randomization of visit timing	•				
CLINICAL / BEHAVIORAL PROCEDURES					
Obstetrical and medical history	•	•	•	•	•
Anthropometry	•	•	•	•	
Blood pressure measurement	•	•	•	•	
Fundal height measurement	•	•	•	•	
Physical exam	•				
Untrained operator scan		•	•	•	
Trained sonographer scan		•	•	•	
LABORATORY PROCEDURES					
Urine storage	•	•	•	•	
Blood storage	•	•	•	•	

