5.0 Research Aims

The FAMLI Technology is a machine learning tool that uses a novel deep convolutional neural network to estimate fetal gestational age from a series of ultrasound blind sweeps. We intend to assess the diagnostic accuracy of the technology by enrolling a cohort of women in early pregnancy, establishing their gestational age by crown-rump length measurement, and then assigning follow-up visits at random times during three gestational age windows. At each of these visits, we will assess gestational age with the FAMLI technology and compare that estimate to the known gestational age established at the baseline ultrasound. Alongside this assessment, we will also conduct standard ultrasound biometry measurements likewise assessing the accuracy of this approach. Our study design will allow precise characterization of the technology's accuracy (against the previously established ground truth) and also allow head-to-head comparison of the FAMLI technology to standard fetal biometry (which is the current gold standard).

Terms:

- **Ground truth** – the gestational age and corresponding estimated date of delivery (EDD) established prior to 14 weeks of gestation and assumed in this protocol to represent a gold standard measurement.
- **Blind sweep** – freehand ultrasound sweeps of the gravid abdomen collected as cineloop video.

- **FAMLI Technology**– the trained deep learning model when deployed on an Android or iOS device and receiving blind sweep ultrasound data from a low-cost probe (e.g., Butterfly iQ+).
- **Untrained operator** – a clinician (e.g., nurse or midwife) with general obstetrics knowledge but with no prior training in sonography.
- **Index test** – a term of art in diagnostic accuracy studies that refers to the test being assessed, in this case the FAMLI Technology.
- **Clinical reference standard** – a term of art in diagnostic accuracy studies that refers to the test against which the index test is evaluated, in this case standard fetal biometry performed by a trained sonographer on a commercial ultrasound machine.
- **Primary evaluation window** – the GA window corresponding to the second trimester of pregnancy (14 $0/7$ through 27 $6/7$ gestational weeks, inclusive). At enrollment each participant will be assigned a random date within this window to return for a study ultrasound evaluation.

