- **Secondary evaluation windows** – the GA windows corresponding to the preterm third trimester (28 $0/7$ through 36 $6/7$ weeks, inclusive) and term gestation (37 $0/7$ through 40 $6/7$ weeks, inclusive). At enrollment each participant will be assigned random dates within these windows to return for a study ultrasound evaluation.

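### Section 6.3.2 does not mask the biometry sonographer to the allocated gestational week or the baseline scan, so the comparator could look too accurate

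*Protocol*

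**What the plan says.** Protocol Section 6.3.2 gives two measures. The first is "The FAMLI Technology software will not be used to assess gestational age at the time of novice or trained sonographer assessment", and the protocol explains it as a protection of sonographer measurement from bias. The second is "We will also train sonographers not to ask participants their due date or last menstrual period prior to commencing the study scan".

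Visit timing is set from ground-truth GA. Under Section 6.3.1, "a participant will have a 1 in 14 chance of being allocated to a given gestational week within the primary evaluation window", and Table 2 gives each week as a seven-day GA range. Then "Women will be allowed to choose their preferred day of participation within the randomized week". Section 5.0 describes the secondary windows in the same way: "At enrollment each participant will be assigned random dates within these windows to return for a study ultrasound evaluation".

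Every participant also has a record that holds the ground truth: "women must have documentation of a baseline scan conducted by a trained sonographer prior to 14 weeks gestation". At each follow-up visit, research staff "measure blood pressure and fundal height", an item listed before the scans.

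I found nothing in the protocol or the SAP that masks the sonographer to the allocated week, the baseline report or due date, earlier study scans, or the fundal height. The SAP has no sensitivity analysis for unmasking.

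**The concern.** The protocol already accepts that knowing GA can bias biometry; that is its reason for keeping the AI off. The remaining rule covers asking, not seeing, and it applies only until the scan starts, not until the measurements are saved.

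The gap matters here because the appointment itself carries the answer. The allocated week and the baseline report both derive from the reference against which biometry is scored. Biometry involves judgement in choosing planes and placing calipers. The index estimate is not produced at the visit and cannot be drawn toward the date in the same way.

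Any bias would therefore run one way. It would lower the comparator's absolute error and raise index minus biometry. The SAP's primary outcome paragraph reads a 95% confidence interval that excludes zero as superiority or inferiority, so a shift of a few tenths of a day can change a primary conclusion. The reported biometry MAE would be wrong too.

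**Working it through.** **Inputs.** From Section 6.8.2: enrolment GA X with mean 74.5 and SD 10.5 days; adjusted biometry estimate −7 + 1.1X with random error SD 4 days; the index test with the same line and random error SD τ; N=400; margin ±2 days. From the SAP: paired Wald 95% interval. Assumed, because the documents give no value: w, the share of biometry error removed by knowing GA.

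**Reproducing the plan.** Biometry error = −7 + 0.1X + ε. Its mean is −7 + 7.45 = 0.45 and its SD is √(1.05² + 4²) = 4.14, so MAE (folded normal) = 3.32 days. At τ=4, simulated equivalence power is 100% at N=200 and N=400, and the two-sided rejection rate is about 5%. Both agree with Table 4. Away from the null, the simulation runs 2 to 10 points above the plan: at a −0.5-day difference it gives about 85%, against the stated 80%. I could not close that gap, and it does not affect the comparison below.

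**What each cue is worth.** These are ceilings on the information, not forecasts of behaviour. They combine a uniform prior (normal approximation) with a 4-day error.

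- Allocated week: prior SD √((7²−1)/12) = 2.0. Combined SD = 1/√(1/16 + 1/4) = 1.79, up to 55% lower. A mid-week guess alone has MAE (3+2+1+0+1+2+3)/7 = 1.7 days.
- Visit number at visit 1: 98 days, prior SD 28.3, combined SD 3.96, about 1% lower. A midpoint guess has MAE 24.5 days.
- Visit number at visit 3: 28 days, prior SD 8.1, combined SD 3.59, about 10% lower.

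**Effect on the primary comparison, N=400.** Biometry error is multiplied by (1−w), so the shift is w × 3.32.

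| w | Shift (days) | False inferior, τ=4 | Superiority power, τ=3.35 (true difference −0.5) | Equivalence, τ=4 |
|---|---|---|---|---|
| 0 | 0 | about 2.5% | about 85% | 100% |
| 5% | 0.17 | about 16% | 54% | 100% |
| 10% | 0.33 | about 50% | about 18% | 100% |
| 30% | 1.00 | 100% | 0% | 100% |
| 50% | 1.66 | 100% | 0% | 68% |

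Simulation runs differ by about a point.

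**Hand check at w=10%, τ=4.** The variance of one absolute error is 4.14² + 0.45² − 3.32² ≈ 6.3. The SE of the mean paired difference is √(6.3 × (1 + 0.9²))/√400 ≈ 0.169. Then 0.332/0.169 ≈ 1.97, and Φ(1.97 − 1.96) ≈ 50%.

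**Alternative form of the pull.** If the estimate moves a fraction f toward mid-week, error becomes (1−f)e + f·u, with u uniform on −3 to 3. MAE is 2.99 at f=0.10 and 2.52 at f=0.25, which gives shifts of 0.33 and 0.80 day.

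**Break-even.** A true 0.5-day advantage disappears at w = 0.5/3.32 = 15%. Moving true equality to the 2-day margin needs w = 2/3.32 = 60%.

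**The case against.** The strongest reply is that nothing shows a sonographer sees any of this. Section 6.3.2 separates the research staff, the untrained operator and the sonographer. Section 6.3.1 has schedules pre-generated by a statistician not otherwise associated with the study. Operating procedures that were not supplied may already mask the sonographer. That stands as far as it goes: a reader might infer that sonographers work with the week in view, and the documents do not say so. However, separate roles and an independent scheduler are not masking, and the text closes none of these routes.

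A reader might also treat all the cues as equal. They are not. At visit 1, the only visit in the primary analysis, visit number adds about 1% and there are no earlier follow-up study scans. The allocated week and the baseline scan are what matter there. Earlier study scans count at visits 2 and 3.

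A third tempting step is to scale from the pilot biometry MAE of 5.4 days, where a 25% pull toward mid-week would cut MAE to about 4.1, a shift of about 1.3 days. That figure comes from a 249-exam test set that Section 4.1.1 does not restrict to the second trimester, and Section 4.0 says biometry error grows with GA. The Section 6.8.2 model is the one given for the primary window. Nothing in the documents supports 25%.

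Finally, the bias is conservative for claiming superiority and at the +2-day bound. That is correct. It does not protect against a false inferior reading, a missed superiority finding, or an understated biometry MAE.

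**Conclusion.** The point holds as a gap in masking at the allocated week and the baseline scan, with earlier study scans added at visits 2 and 3. It does not show that bias occurred or will occur.

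The exposed result is the superiority or inferiority reading. A cut of only 5% to 10% in biometry error is enough to alter it materially at N=400. A reader might conclude that the ±2-day equivalence claim is also in doubt. Under true equality it is not, up to about a 30% cut. Equivalence is touched in one other case: if the index test is truly better by about 2 days or more, the same bias would pull the difference back inside the margin and make a false equivalence finding more likely.

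The direction follows from the design. The sizes rest on the Section 6.8.2 error model and on assumed values of w, which the documents cannot supply. The change is worth making before data collection, because this kind of bias cannot be removed afterwards.

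**What to change.** Add to Section 6.3.2: until biometry is saved and locked, the sonographer is not shown the allocated week, the due date or LMP, the baseline report, the fundal height from the same visit, or earlier study scans. Leave the LMP and due-date fields on the machine blank, and hide GA readouts where the machine allows. If existing procedures already do this, one sentence saying so settles the point.

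Record any unmasking before locking. In the SAP, add a sensitivity analysis that repeats the primary comparison without those scans, with the caveat that they may be selected for complications, since that is when records are most likely to be opened.

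The cost is a change to the operating procedure and machine preset, plus one case report form item. The sample size is unchanged. Masking ends once biometry is saved, and clinical reporting and referral rules are not altered.
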